9.6 Prohibited medication and procedures

The following medications are prohibited during the trial from randomisation through Week 52 (or Week 68):

- TCS of any WHO class (except for subjects in open-label treatment).
- Other topical medications used for the treatment of AD, such as TCI.
- Use of ultraviolet A or B (UVA or UVB), psoralen + UVA (PUVA), other phototherapy, or tanning beds.
- Prescription emollients or emollients containing additives such as ceramide, hyaluronic acid, urea, or filaggrin (unless treatment was initiated prior to screening).
- Three or more bleach baths per week.

Any prohibited topical treatments must be recorded as concomitant medication.

The following medications are prohibited during the trial from randomisation through safety follow-up (FU1 [Week 66] or FU2 [Week 82]):

• Investigational agents other than tralokinumab

- Immunoglobulin or blood products
- Systemic corticosteroids (nasal and inhaled corticosteroids are allowed)
- Systemic treatment for AD with an immunosuppressive/ immunomodulating agent (e.g., cyclosporine, mycophenolate mofetil, azathioprine, methotrexate, Janus kinase inhibitors, interferon-gamma, or other biologics)
- Allergen immunotherapy
- Live (attenuated) vaccine

The sponsor's medical expert must be notified if a subject receives any of these medications during the trial.

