9.5 Concomitant medication and procedures

Any medication or vaccine that the subject receives from 3 months prior to screening through safety follow-up (FU1 [Week 66] or FU2 [Week 82]) must be recorded in the subject's medical record and the eCRF along with details such as:

- Reason for use.
- Dates of administration including start and stop dates.
- Dosage information including dose and frequency.
- For topical treatments: size of treated area ($\leq 250 \text{ cm} 2 \text{ or } > 250 \text{ cm} 2$).

Similarly, concomitant procedures (including body location, diagnosis, and start and stop date) must also be recorded in the subject's medical record and the eCRF. Note: in this trial, only surgical procedures will be recorded.

Investigators may prescribe concomitant medications or treatments to provide adequate supportive care as deemed necessary, except for medications listed in Section 9.6. The

Trial ID: LP0162-1325	Date: 14-Aug-2018	Version: 4.0
		Page 58 of 169

sponsor's medical expert should be contacted if there are any questions regarding concomitant or prior therapy.

Concomitant medication for conditions other than AD may be continued throughout the trial without any change in dosage whenever possible.

The following concomitant medications related to AD treatment are permitted from screening through safety follow-up (FU1 [Week 66] or FU2 [Week 82]):

- Oral antibiotics, antiviral, or antifungal therapy for skin infections as appropriate.
- Stable doses of an emollient (see Section 9.4 for allowed emollients; subjects must apply such emollients twice daily [or more, as needed] for at least 14 days before baseline and throughout trial participation).
- Oral anti-histamines.

In addition, the use of topical treatments is permitted during safety follow-up (from Week 52 or Week 68) at the investigator's discretion.

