9.7 Rescue treatment

Initial treatment period and maintenance treatment period

If medically necessary (i.e., to control intolerable AD symptoms), rescue treatment for AD may be provided to trial subjects at the discretion of the investigator. For the purpose of efficacy analysis, subjects who receive rescue treatment during the initial treatment period will be considered as non-responders, but they will continue IMP treatment if rescue consisted of topical medications.

TCI may be used for rescue, but should be reserved for problem areas only, for example face, neck, intertriginous and genital areas, etc. If possible, investigators should attempt to limit the first step of rescue therapy to topical medications, and escalate to systemic medications only for subjects who do not respond adequately after at least 14 days of topical treatment.

If a subject receives rescue treatment with systemic corticosteroids or non-steroidal systemic immunosuppressive drugs (cyclosporine, methotrexate, mycophenolate mofetil, azathioprine, etc.), IMP will be immediately discontinued (see Section 9.8.2, reasons for temporary discontinuation of IMP). After the treatment with these medications is completed, IMP may be resumed if deemed appropriate by the investigator and sponsor's medical expert, but not sooner than 5 half-lives after the last dose of systemic rescue medication.

Investigators should make every attempt to conduct efficacy and safety assessments (for example disease severity scores, safety labs) immediately before administering any rescue treatment. An unscheduled visit may be used for this purpose, if necessary.

Trial ID: LP0162-1325	Date: 14-Aug-2018	Version: 4.0
		Page 60 of 169

Open-label tralokinumab arm only

From Week 16 through safety follow-up (FU1 [Week 66] or FU2 [Week 82]) subjects may use mild to moderate strength TCS and/or TCI as needed (prn usage) on lesional skin at the investigator's discretion (see Appendix 9 for TCS classification and examples). Use of TCS and TCI should be recorded as concomitant medication.

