#### Efficacy analyses open-label period

For the open-label treatment period IGA, EASI75, EASI and SCORAD will be summarised by visit and initial treatment for subjects who transferred to open-label treatment at Week 16,

Trial ID: LP0162-1325	Date: 20-May-2019	Version: 1.0
		Page 20 of 31

and by week since transfer to open-label and at Week 52, by previous maintenance treatment for subjects who transferred to open-label treatment after Week 16. IGA, EASI and SCORAD for subject who transferred to open-label treatment at Week 16 and IGA for subject who transferred to open-label treatment after Week 16 will be presented in figures.

Trial ID: LP0162-1325	Date: 20-May-2019	Version: 1.0
		Page 21 of 31

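### Sections 9.6 and 9.7 give opposite rules on TCI for open-label subjects between Week 16 and Week 52 (or 68)

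*Protocol*

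**What the plan says.** Protocol Section 9.6 has a first list of prohibited treatments that runs from randomisation through Week 52, or Week 68 where the short-term extension applies. Two entries matter here. The TCS entry carries an exception: "TCS of any WHO class (except for subjects in open-label treatment"). The next entry carries none: "Other topical medications used for the treatment of AD, such as TCI".

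Protocol Section 9.7, under its sub-heading for the open-label tralokinumab arm, says that "subjects may use mild to moderate strength TCS and/or TCI as needed (prn usage) on lesional skin at the investigator's discretion". That permission starts at Week 16 and runs through the safety follow-up visit at Week 66 or 82.

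Protocol Section 9.5 allows investigators to prescribe supportive treatment "except for medications listed in Section 9.6". It permits topical treatments at the investigator's discretion once safety follow-up begins.

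Elsewhere (for example Protocol Sections 5.6, 7.1 and 9.8.1) the open-label arm is described as tralokinumab Q2W with optional TCS, and the label in SAP Section 6.8.8 follows suit. Neither mentions TCI.

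For analysis, SAP Section 6.6.5 states: "For the open-label treatment period IGA, EASI75, EASI and SCORAD will be summarised by visit and initial treatment" for subjects who moved to open label at Week 16, with a corresponding summary for later transfers.

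**The concern.** A site that works from 9.6 would withhold TCI from an open-label subject, or record its use as a deviation. A site that works from 9.7 would allow it and record an ordinary concomitant medication. Appendix 4D of the protocol requires deviations to be documented, assessed for serious breach and reported in the clinical trial report, so the classification has consequences. If practice differed between sites, background topical treatment in the open-label arm would differ with it, and so would the IGA, EASI and SCORAD summaries for that period. The rescue tables in SAP Section 6.3 cover only the initial and maintenance periods, so they would not show open-label TCI use.

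**Working it through.** **The two sections side by side, for an open-label subject**

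| Item | Section 9.6 | Section 9.7 |
|---|---|---|
| TCI | Prohibited, no open-label exception | Permitted as needed |
| TCS, mild to moderate | Ban lifted | Permitted as needed |
| TCS, stronger | Ban lifted, no strength stated | Outside the stated permission |
| Period | Randomisation to Week 52 (or 68) | Week 16 to Week 66 (or 82) |

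The TCI row cannot be satisfied both ways. For a subject entering open label at Week 16, the overlap lasts 52 − 16 = 36 weeks, or 68 − 16 = 52 weeks with the extension. After that the 9.6 list has ended and 9.5 permits topical treatment, so the conflict stops.

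The TCS rows can be read together: 9.6 removes a ban and 9.7 says what may be used. The gap is that 9.6 alone gives no hint of a strength limit.

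**How many subjects the clause governs**

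The documents state no open-label share, so it has to be derived. Inputs:
- 780 randomised 3:1, 585 to tralokinumab and 195 to placebo (Protocol Section 12.1).
- About 40% of tralokinumab subjects re-randomised at Week 16 (Section 7.2).
- Placebo response of 15% for EASI75 and 10% for IGA 0/1 (Section 12.1).
- Non-responders at Week 16 go to open label; response is IGA 0/1 or EASI75 (Section 7.1).

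Check of the plan's own figures: 780 × 3/4 = 585 and 780 × 1/4 = 195. Expected responders are 0.40 × 585 = 234 (plan: 235) and 0.30 × 585 = 175.5 (plan: 175). Both agree within rounding.

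Share entering open label at Week 16 = [585 × (1 − r_T) + 195 × (1 − r_P)] / 780, where r_T and r_P are the tralokinumab and placebo response rates.

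- r_T = 40%, r_P = 15% (every placebo IGA responder also reaches EASI75): 351 + 165.75 = 516.75, and 516.75 / 780 = 66.3%.
- r_T = 40%, r_P = 15% + 10% = 25% (no overlap between the two placebo criteria): 351 + 146.25 = 497.25, and 497.25 / 780 = 63.8%.

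The documents give no dropout rate. As an assumption, suppose 5% or 10% of all subjects leave before Week 16, all of them non-responders. The first figure then becomes (516.75 − 39) / 780 = 61.3% or (516.75 − 78) / 780 = 56.3%. Later transfers from maintenance would add to any of these.

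**What the conflict can reach**

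- Week 16 endpoints: the IMP is given last at each visit (Section 10.1), so these are assessed before open-label treatment starts.
- Week 52 maintenance endpoints: subjects transferred to open label already count as non-responders (Section 12.3.6.1), whatever topical treatment they then use.
- Per protocol set: its criteria (Section 12.2) do not use concomitant medication, and it serves only the primary endpoints up to Week 16.
- Open-label IGA, EASI75, EASI and SCORAD: descriptive summaries, which differing TCI use could influence.

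**The case against.** The best counter-argument is that 9.7 is the specific provision and 9.6 the general list. Section 9.6 also bans TCS, TCI and systemic agents in the blinded periods without mentioning rescue, yet 9.7 provides for rescue with them. So 9.6 cannot be absolute, and 9.7 could be taken to override it throughout. In addition, the Amendment 3 table gives a rationale for the 9.7 sentence that agrees with its current text, which suggests that 9.6 missed a conforming edit. Section 9.5 also offers the sponsor's medical expert for questions.

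Part of this stands. It is a plausible account of how the mismatch arose, and it makes an even split of sites between the two sections unproven. It does not remove the conflict. Section 9.6 does address open-label subjects, and it confines its exception to TCS; a reader would take its silence on TCI as deliberate. No sentence gives 9.7 precedence, and 9.5 names 9.6 as the list of what may not be prescribed. The open-label permission is also for as-needed use and lacks the medical-necessity condition attached to rescue in the blinded periods.

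It is also fair to say that TCI use is recorded under either section, so it can be described from the concomitant medication data, and that a short table label need not list every permitted treatment. Both points stand.

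**Conclusion.** The TCI conflict is real, lies in current operative text, and should be corrected. It affects consistency of site conduct, classification of deviations and interpretation of descriptive open-label summaries.

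Three stronger readings might be inferred, and the documents do not support them.
- **That about two thirds of subjects are affected.** The 64% to 66% is the planned share entering open label at Week 16 before dropout. It rests on the plan's 40% re-randomisation rate and on placebo overlap between none and complete. Only subjects for whom TCI is considered meet the conflict, and no rate for that is given.
- **That the TCS rules also contradict each other.** Lifting a ban and then stating a permitted strength are compatible. What is missing is a cross-reference.
- **That the efficacy conclusions are at risk.** Neither the Week 16 nor the Week 52 confirmatory analyses use data that the open-label TCI rule could change.

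The size of any effect on deviation counts or on the open-label summaries cannot be calculated from the documents.

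**What to change.** Reconcile Protocol Sections 9.6 and 9.7 so that both state one rule for TCI in open-label treatment; which rule is for the sponsor to decide. Add a cross-reference from the TCS entry in 9.6 to the strength limit in 9.7. Classify protocol deviations against the single TCI rule for all sites. If TCI is allowed, say so in the open-label arm description or in a footnote to the treatment label in SAP Section 6.8.8.

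The cost is wording in the protocol, with the usual amendment handling, and at most a footnote in the SAP. No new data or analyses are needed.

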9.7 Rescue treatment

Initial treatment period and maintenance treatment period

If medically necessary (i.e., to control intolerable AD symptoms), rescue treatment for AD may be provided to trial subjects at the discretion of the investigator. For the purpose of efficacy analysis, subjects who receive rescue treatment during the initial treatment period will be considered as non-responders, but they will continue IMP treatment if rescue consisted of topical medications.

TCI may be used for rescue, but should be reserved for problem areas only, for example face, neck, intertriginous and genital areas, etc. If possible, investigators should attempt to limit the first step of rescue therapy to topical medications, and escalate to systemic medications only for subjects who do not respond adequately after at least 14 days of topical treatment.

If a subject receives rescue treatment with systemic corticosteroids or non-steroidal systemic immunosuppressive drugs (cyclosporine, methotrexate, mycophenolate mofetil, azathioprine, etc.), IMP will be immediately discontinued (see Section 9.8.2, reasons for temporary discontinuation of IMP). After the treatment with these medications is completed, IMP may be resumed if deemed appropriate by the investigator and sponsor's medical expert, but not sooner than 5 half-lives after the last dose of systemic rescue medication.

Investigators should make every attempt to conduct efficacy and safety assessments (for example disease severity scores, safety labs) immediately before administering any rescue treatment. An unscheduled visit may be used for this purpose, if necessary.

Trial ID: LP0162-1325	Date: 14-Aug-2018	Version: 4.0
		Page 60 of 169

Open-label tralokinumab arm only

From Week 16 through safety follow-up (FU1 [Week 66] or FU2 [Week 82]) subjects may use mild to moderate strength TCS and/or TCI as needed (prn usage) on lesional skin at the investigator's discretion (see Appendix 9 for TCS classification and examples). Use of TCS and TCI should be recorded as concomitant medication.

9.8 Dose modification and IMP discontinuation rules

9.8.1 Reasons for permanent discontinuation of IMP

Subjects will be permanently discontinued from IMP in the event of:

- Anaphylactic reaction or other severe systemic reaction to IMP injection.
- An AE that, in the opinion of the investigator or sponsor's medical expert, contraindicates further dosing.
- Diagnosis of a malignancy during the trial, excluding carcinoma in situ of the cervix, or localised squamous or basal cell carcinoma of the skin.
- Evidence of pregnancy.
- Any infection that is opportunistic, such as active tuberculosis and other infections whose nature or course may suggest an immuno-compromised status.
- Severe laboratory abnormalities:
 - ALT and/or AST values >3x ULN with total bilirubin >2x ULN (unless elevated bilirubin is related to Gilbert-Meulengracht Syndrome)
 - Confirmed AST and/or ALT >5x ULN (for more than 2 weeks)

Subjects in open-label treatment (tralokinumab 300 mg Q2W with optional use of TCS) who in the opinion of the subject or investigator have unacceptable treatment effect of tralokinumab may discontinue open-label treatment and enter the safety follow-up period.

9.8.2 Reasons for temporary discontinuation of IMP

IMP dosing may be temporarily suspended in the event of:

- Other intercurrent illnesses or major surgery.
- An infection that requires parenteral treatment with antibiotic, antifungal, antiviral, anti-parasitic, or anti-protozoal agents.
- Treatment with systemic corticosteroids or non-steroidal immunosuppressive/immunomodulating medications (e.g., cyclosporine, methotrexate, azathioprine, mycophenolate mofetil, Janus kinase inhibitors, biologic agents).

IMP dosing may resume after the medication leading to suspension of IMP is discontinued.

A decision to discontinue IMP temporarily or to reinstitute IMP treatment must be discussed with sponsor's medical expert. However, the investigator may suspend trial treatment at any time, even without consultation with sponsor's medical expert if the urgency of the situation requires immediate action and if this is determined to be in the subject's best interest. In such cases, sponsor's medical expert should be informed as soon as possible.

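### Protocol Sections 9.7 and 9.8.2 are inconsistent on stopping and restarting IMP after systemic rescue treatment

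*Protocol*

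**What the plan says.** Protocol Section 9.7, in the part headed for the initial and maintenance treatment periods, deals with systemic corticosteroids and non-steroidal systemic immunosuppressants given as rescue. It says "IMP will be immediately discontinued (see Section 9.8.2, reasons for temporary discontinuation of IMP". On restart it says "IMP may be resumed if deemed appropriate by the investigator and sponsor's medical expert", and adds the limit "but not sooner than 5 half-lives after the last dose of systemic rescue medication".

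Protocol Section 9.8.2, the target of that cross-reference, opens with "IMP dosing may be temporarily suspended in the event of". One of the listed reasons is "Treatment with systemic corticosteroids or non-steroidal immunosuppressive/immunomodulating medications", with examples that include the drugs named in 9.7 and also Janus kinase inhibitors and biologic agents. Its restart sentence is "IMP dosing may resume after the medication leading to suspension of IMP is discontinued". It also requires that a decision to suspend or restart be discussed with the sponsor's medical expert; the only exception is urgent suspension.

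Section 9.8.2 does not mention the 5 half-lives, does not point back to 9.7, and does not say which section prevails. The open-label part of 9.7 speaks only of topical treatment.

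**The concern.** For the same drugs, one section obliges the site to stop IMP and the other permits it to. One section sets a minimum time before restart and the other sets none. The cross-reference runs only from the fuller text to the shorter one, so someone who opens 9.8.2 directly, as the section on temporary discontinuation, never meets the 9.7 conditions.

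The rule protects subjects who have just received systemic immunosuppression, and it must be applied at approximately 130 sites (Protocol Section 7.2). It also bears on the data. Whether an early restart is a protocol deviation depends on which section is read, and deviations are reported in the clinical trial report (Appendix 4D). The number of doses received, and hence adherence, depends on it too, as do observations after rescue wherever these are used.

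**Working it through.** No figure in the plan needs reproducing, so the check is a comparison of the two texts followed by a sizing of the difference.

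**Step 1: the texts side by side**

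| Element | Section 9.7 | Section 9.8.2 |
|---|---|---|
| Stopping IMP | Mandatory: "IMP will be immediately discontinued" | Optional |
| Earliest restart | 5 half-lives after the last rescue dose | Once the other medication is discontinued; no minimum |
| Role of sponsor's medical expert in restart | Must, with the investigator, find it appropriate | Must be consulted |
| Drugs | Systemic corticosteroids and named immunosuppressants; open list | The same, plus Janus kinase inhibitors and biologics as examples; open list |
| Circumstances | Rescue for atopic dermatitis | Any use of these drugs; also intercurrent illness, surgery and infections |
| Periods | Initial and maintenance | Not limited |
| Reference to the other section | Yes | No |

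The first two rows are the inconsistency. The rows on drugs and periods show two gaps in scope. The SAP's rescue algorithm (Section 6.3) counts dupilumab, so rescue with a biologic is foreseen, yet 9.7 does not name biologics. For subjects in open-label treatment, 9.8.2 is the only restart text.

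**Step 2: size of the restart difference**

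Earliest restart after the last rescue dose is 5 × t½ under 9.7, and no stated minimum under 9.8.2 read alone. The largest difference is therefore

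gap (days) = 5 × t½, and gap / 14 = number of two-week dosing intervals.

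The 14-day interval comes from Protocol Section 9.2. The rescue drug's half-life is not in the documents, so the values below are assumptions spanning a range.

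| Assumed t½ (days) | Gap (days) | Gap / 14 | Dose slots affected |
|---|---|---|---|
| 0.125 | 0.625 | 0.04 | 0 or 1 |
| 1 | 5 | 0.36 | 0 or 1 |
| 2.8 | 14 | 1.0 | 1 |
| 7 | 35 | 2.5 | 2 or 3 |
| 14 | 70 | 5.0 | 5 |

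The gap equals one interval when 5 × t½ = 14, that is t½ = 14 / 5 = 2.8 days. Below that it is less than one interval.

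The optional wording on stopping adds a second difference, in doses given during the rescue course itself. The documents set no course length, so it cannot be sized.

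**Step 3: where it reaches the analyses**

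- Primary composite estimand (Protocol 12.3.5.1.1): subjects rescued before Week 16 are non-responders whatever happens to IMP afterwards.
- Maintenance estimand (12.3.6.1): the same, for rescue before Week 52.
- Hypothetical estimands (12.3.5.1.2 and 12.3.5.2.1): data after rescue are not used.
- Treatment-policy estimands (12.3.5.1.3 and 12.3.5.2.2): data are used regardless of rescue, so restart timing can influence them.
- Exposure time (SAP 6.5 and 6.8.2) runs from start to end of each period. A temporary gap does not shorten it; doses received and adherence are what change.

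**The case against.** The strongest defence is that the two sections can be obeyed together. The 9.8.2 wording is permissive and general; 9.7 is specific to rescue. A site that follows the 9.7 conditions breaches neither, and a site that restarts earlier after systemic rescue in the initial or maintenance period breaches 9.7. This stands. A reader might infer that two sites could both comply and yet treat the same subject differently; for those two periods the documents do not support that. The defect is that 9.8.2 omits the 9.7 conditions, so a site could cite 9.8.2 for an earlier restart.

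Second, sites do not restart on their own reading. Both sections involve the sponsor's medical expert, and Section 9.6 requires that expert to be notified when prohibited systemic treatments are used. This limits divergence, but the expert works from the same two texts.

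Third, a reader might infer that restart times would differ greatly. The only half-life derivable from the documents is that of IMP itself: inclusion criterion 11 equates 16 weeks with 5 half-lives, so 112 / 5 = 22.4 days. Applied to a biologic rescue drug, that gives a gap of 112 days, or 8 dosing intervals. But this borrows the half-life of IMP for a class that 9.7 does not name, and it sits at the far end of an assumed range. For a drug with a half-life of 1 day the gap is 5 days.

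Fourth, the differing drug lists are not in themselves a contradiction, since both are open. That is correct; what remains is uncertainty about scope.

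Finally, the SAP (Section 6.8.2) puts the data cut-off at 11 April 2019, with the subjects then ongoing being in the short-term extension. An amendment after that date would reach few subjects under the 9.7 rule. This affects the form of the remedy, not the finding.

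**Conclusion.** The inconsistency is real and can be read directly from the two sections: mandatory against optional stopping, and a minimum wait against none. Its largest effect on restart timing is 5 half-lives of the rescue drug, which exceeds one dosing interval only for half-lives above 2.8 days. That size rests on assumed half-lives and on a reader using 9.8.2 alone. The documents give no frequency for systemic rescue, so no effect on adherence or deviation counts can be quantified.

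The consequences lie mainly in subject management, actual dosing, deviation classification and the supplementary treatment-policy analyses. The primary and maintenance conclusions do not turn on it. It should be corrected because it is a subject-safety rule and correction is cheap. Nothing here says which of the two rules is clinically right.

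**What to change.** Reconcile Sections 9.7 and 9.8.2 into a single stop and restart rule, placed in one section, with the other referring to it. The rule should carry one drug list that settles whether Janus kinase inhibitors and biologics are included. It should state whether it covers only rescue or any use of these drugs, and whether it applies in open-label treatment and the short-term extension. The sponsor's medical expert should decide the clinical content.

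The cost is protocol wording at the next amendment and a notice to sites. Sample size, significance levels and analysis methods are unchanged. If no subject remains on IMP when this is taken up, record in the clinical trial report which section was used to classify restarts after systemic rescue as deviations.
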